2.5 Preliminary Data

2.5.1 Biomarkers of Intestinal Integrity

Plasma citrulline is a plasma biomarker of intestinal integrity in adults undergoing HCT and in pediatric conditions.⁵⁷⁻⁶¹ To determine the association of plasma citrulline and intestinal integrity in children undergoing alternative donor alloHCT, we measured plasma citrulline levels in 10 children and adolescents beginning at the start of conditioning therapy and then every three to seven days.⁶² The mean citrulline value prior to the initiation of treatment was 20.1 ± 7 μmol/L. The greatest decrease in mean plasma citrulline occurred between the initiation of conditioning and the day of hematopoietic graft infusion (Day 0, 7.1 ± 4.9 μmol/L) and reached a maximal mean nadir at Day 7 (6.6 ± 5.3 μmol/L). Levels did not begin to recover to pre-transplant levels until Day 21 (10 ± 3.7 μmol/L). Significant associations were found between plasma citrulline levels and the odds of developing mucositis (OR = 0.88, 95% CI=0.79–0.99, *p*=0.036) and diarrhea (OR=0.70, CI=0.59–0.84, *p*<0.0001). These results lend further support that plasma citrulline is a marker of GI integrity following alternative donor alloHCT. Moreover, we have identified a therapeutic window in which an intervention may prevent the decline in GI integrity as measured by plasma citrulline levels during HCT.

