The citrulline levels at each of the time points will be summarized and described by arm. The mean quantitative change in citrulline level from start of conditioning to each of the four later time points will be compared between the 2 arms to determine if *LBP* administration maintains citrulline level via two-sample t-test and repeated-measures general linear modeling which include adjustments for potential confounders. In such analyses, multiple comparison adjustments for the 4 parallel analyses (linear contrasts) will be performed with Bonferroni adjustment to maintain an overall fixed α level. Linear mixed models, which include data from all time points for longitudinal data analyses with adjustment for within-patient correlation, will also be considered.

Likewise, we will compare the incidence of MBIs between two groups looking at the time from start of protocol treatment to first infection as the primary endpoint. Patients without infection will be censored when they meet criteria to be off study. Cox proportional hazards regression will be used to compare the incidence density of infection for the two groups adjusted for confounders (use of total body irradiation, duration of broad spectrum antibiotic usage, incidence of *C. difficile* infection, and duration of total parenteral nutrition). Main analyses for this aim will be based on a modified intention-to-treat principle (inevaluable patients will be excluded), but additional as-treated analysis, subset analysis, or sensitivity analysis may be performed if we observe issues with adherence to the randomized treatment on the study.

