Exploratory Aims 3 and 4: These aims will examine the effects of *LBP* introduction on the intestinal flora of pediatric alloHCT recipients. The association between *LBP* administration and bacterial genes and pathways, and bacterial metabolites will be evaluated with Pearson's correlation coefficient with possible transformation to approximate normality. In addition to confirming the significance, a 95% confidence interval will be estimated for each marker. The total length of the interval depends on the observed correlation; the length will be 0.53 if the correlation is 0.40 and 0.24 if the correlation is 0.8. In addition to correlation, bivariate scatterplots will be used to display the association between *LBP* administration and each marker. Finally, we will perform a descriptive analysis examining the association between GvHD outcomes and bacterial genes, pathways, and metabolites using Cox regression. Additional regression models will adjust for other known GvHD risk factors.

Exploratory Aim 5: This aim will examine the effects of *LBP* on pro-inflammatory cytokines in alloHCT recipients. We hypothesize that *LBP*-associated maintenance or restoration in the microbiota will attenuate serum levels of pro-inflammatory cytokines in the early post-transplant period. We will use the same analytic approach as described for exploratory Aim 2 above.

Exploratory Aim 6: This aim will examine the effects of LBP on the incidence (yes/no) of *Clostridium difficile*-associated diarrhea in alternative donor HCT patients. Patients who have at least one incidence (positive) of *C. diff* during any reporting period is considered evaluable for this aim. We will compare proportion of *C. diff* during the study period between arms via the chi-square test.

Exploratory Aim 7: This aim will examine whether LBP administration reduces hospital days within the first 120 days post hematopoietic cell transplant. Total hospital days over the study period is calculated as the duration between the date of admission for conditional therapy and the date of discharge (or the study end date). Hospital days will be compared between arms by t-test (or Wilcoxon rank-sum test if assumptions for t-test are not met).

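### Exploratory Aims 2 and 5 compare arms on change from baseline without naming the baseline value as a covariate, and so may lose precision that the samples already collected would give.

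*Combined protocol and SAP*

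**What the plan says.** Section 9.3, Exploratory Aim 2, states that "The mean quantitative change in citrulline level from start of conditioning to each of the four later time points will be compared" between the two arms "via two-sample t-test and repeated-measures general linear modeling which include adjustments for potential confounders". The confounders for the citrulline model are not listed. The same section adds: "Linear mixed models, which include data from all time points for longitudinal data analyses with adjustment for within-patient correlation, will also be considered". It does not say how the baseline value would enter such a model.

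For the cytokines in Exploratory Aim 5: "We will use the same analytic approach as described for exploratory Aim 2 above".

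Sections 7.1 and 7.4.1 schedule a blood sample on the first day of conditioning or in the 72 hours before it, so a baseline value is planned for every patient. Section 9.4 bases the citrulline power on a two-sample t-test at two-sided 0.0125. It quotes detectable effects of 0.4 SD (confirmatory stage) and 0.7 SD (screening stage), without saying which SD is meant.

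The only variability data are in Section 2.5.1: "we measured plasma citrulline levels in 10 children and adolescents beginning at the start of conditioning therapy". There, "The mean citrulline value prior to the initiation of treatment was 20.1 ± 7", and the mean "reached a maximal mean nadir at Day 7 (6.6 ± 5.3") µmol/L. Day 0 was 7.1 ± 4.9 and Day 21 was 10 ± 3.7.

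**The concern.** A change score subtracts the whole baseline value, which is right only if the slope of follow-up on baseline is 1. In the pilot, baseline citrulline has the largest raw SD of the four time points reported, so full subtraction can add more noise than it removes. A model with baseline as covariate estimates the slope instead of fixing it at 1.

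Under randomization both approaches estimate the same arm difference, so the issue is precision and not bias. Citrulline is the protocol's chosen serum measure of intestinal integrity (Sections 1.2.2 and 7.3.1), which is central to the proposed mechanism. A less precise analysis makes it easier to miss a real effect there, especially if the trial ends after the screening stage with few patients sampled.

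**Working it through.** **The plan's own figures.** With samples from 80% of patients, 0.8 × 227 gives about 181 per arm and 0.8 × 60 = 48 per arm. At two-sided 0.0125 (critical value 2.498):

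- 0.4 SD, 181 per arm: 0.4 × √(181/2) = 3.81, and 3.81 − 2.50 = 1.31, so power is 90% (0.904 normal, 0.902 noncentral t).
- 0.7 SD, 48 per arm: 0.7 × √(48/2) = 3.43, and 3.43 − 2.50 = 0.93, so power is about 82% (0.824 normal, 0.809 noncentral t).

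Both stated effect sizes are reproduced as detectable with at least 80% power.

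**Variance ratio.** Let s0 be the baseline SD, s1 the follow-up SD, r their correlation and k = s0/s1.

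- Var(change) = s0² + s1² − 2·r·s0·s1
- Var(baseline-adjusted) = s1²(1 − r²)
- Ratio = 1 + (k − r)²/(1 − r²)

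The ratio is never below 1. If k > 1, its minimum over r is k², reached at r = 1/k. If k ≤ 1, its minimum is 1, reached at r = k.

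**Citrulline, raw scale, pilot SDs** (r is not given in the documents, so it is varied):

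| r | Day 0 (4.9) | Day 7 (5.3) |
|---|---|---|
| 0 | 3.04 | 2.74 |
| 0.3 | 2.40 | 2.14 |
| 0.5 | 2.15 | 1.90 |
| 0.7 | 2.04 | 1.76 |
| minimum over all r | (7/4.9)² = 2.04 | (7/5.3)² = 1.74 |

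A simulation at Day 7 with r = 0.757, where the minimum lies, gave 1.76. For Day 21 the minimum is (7/3.7)² = 3.58, but Day 21 is not a sampling day in this trial.

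In patient numbers: a difference of 0.4 SD of change at 90% power takes 179 per arm on change, and at most 103 per arm at Day 7 with baseline adjustment.

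**If the SDs were equal** (k = 1), the ratio is 2/(1 + r): 1.54 at r = 0.3, 1.33 at 0.5 and 1.18 at 0.7.

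**Log scale.** Assuming lognormal values, log SD = √ln(1 + (SD/mean)²):

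- baseline: SD/mean = 7/20.1 = 0.35, log SD 0.34
- Day 0: 4.9/7.1 = 0.69, log SD 0.62
- Day 7: 5.3/6.6 = 0.80, log SD 0.71

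Baseline is now the less variable measurement, so k < 1. At r = 0, 0.3, 0.5 and 0.7 the ratio is 1.29, 1.06, 1.00 and 1.05 at Day 0, and 1.23, 1.04, 1.00 and 1.10 at Day 7.

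**Uncertainty in the SDs.** With 10 patients, a 95% interval for the Day 7 raw variance ratio s0²/s1² runs from about 0.4 to 7 by the F distribution, and from 0.5 to 6.5 allowing for r = 0.5. It includes 1.

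**The case against.** The strongest reply is that the plan leaves baseline adjustment unspecified and does not exclude it. The repeated-measures model adjusts for unnamed confounders, and a mixed model may be used. That stands as far as it goes: if baseline were entered as a covariate, modelling change or the follow-up value would give the same arm estimate. But the t-test on change has no covariate under any reading. The confounders listed in the same aim for bloodstream infection are total body irradiation, antibiotic duration, *C. difficile* and parenteral nutrition, with no baseline marker value. A mixed model that treats baseline as one more outcome, with free means in each arm, reproduces the change contrast when data are complete.

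Three stronger readings are tempting, and the documents do not support them.

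- *That 1.7 applies to cytokines as well.* No cytokine SD appears anywhere. A marker that varies more after transplant than before has a minimum ratio of 1.
- *That 1.7 is a firm lower bound.* It holds over every correlation but treats SDs from 10 patients as exact. It also rests on plasma where the trial uses serum, on the raw scale, and on two of the trial's sampling days. No SDs are given for Days 14, 28 or 56. A Day 7 SD/mean of 0.8 in a non-negative marker suggests skew, and taking logs removes most of the gain at Days 0 and 7.
- *That the trial needs more patients or is underpowered for citrulline.* The primary aim sets the sample size, and the effects stated in Section 9.4 are met. One can build a sharp contrast, such as 52% against 89% power for a Day 7 difference of 2 µmol/L at r = 0.3 with 181 per arm. Neither the 2 µmol/L nor the correlation comes from the documents. At 3 µmol/L with r = 0.3, or 2 µmol/L with r = 0.7, the change-score test itself reaches about 90%.

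**Conclusion.** The point holds as an improvement to the specified analysis. The named comparison is change from start of conditioning, and baseline is not named as a covariate although it is collected. Adjusting for it is never less precise in large samples.

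The size of the gain is uncertain. For raw citrulline at the pilot point SDs, the variance of the change-score t-test is at least 1.7 times that of the adjusted analysis at Day 7 and 2.0 times at Day 0. It is about 1.2 to 1.5 times if the SDs are equal and r lies between 0.3 and 0.7, and about 1.0 to 1.3 times on a log scale at Days 0 and 7 for r from 0 to 0.7. For cytokines only the general result applies. The figures assume that the pilot ± values are SDs. The consequence is limited to precision in exploratory aims. The primary analysis and the sample size are unaffected.

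**What to change.** In Section 9.3, for citrulline and for each cytokine or biomarker, state that arms are compared at each time point in a model of the post-baseline value with the patient's own baseline value as covariate. This can be ANCOVA at each visit, or a mixed model with baseline and baseline-by-visit terms. Report change from baseline descriptively. Choose raw or log scale by skewness, as a decision separate from the efficiency argument, and state it in advance. In Section 9.4, say which SD the 0.4 and 0.7 refer to.

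The cost is SAP wording only: no new samples, visits or patients. If logs are used, arm differences are read as ratios.

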7.4 Specimen Collection, Processing and Shipping

7.4.1 Blood Specimens (Citrulline and Cytokines)

Sample Time Points:
	
 • First day of conditioning or anytime within 72 hours before the start of conditioning (prior to chemotherapy) • Day 0 (graft infusion) • Day 7 • Day 14 • Day 28 or discharge, whichever is first • Day 56 (citrulline only) 
Sample acquisition can occur within 72 hours before the first day of conditioning. Sampling can occur within 24 hours before or after designated collection times for D0, D7, D14, D28 without being considered a protocol deviation. D56 sampling can occur within 14 days without being considered a deviation.
								

Blood Collection Procedure:
	
Draw 6 mL of whole blood in a red top tube (supplied by site).
								

Specimen Processing:
	
 1. After collection, allow blood to coagulate at room temperature. 2. After coagulation (but within 1 hour after collection) centrifuge the blood samples at 4°C for 15 minutes at 3000 rpm. 3. Aliquot the serum (upper layer) into three 1.5 mL cryovials (0.5 mL of serum per aliquot). 4. Store frozen at -80°C (or -70°C) immediately after aliquoting. 								

Specimen Labeling:
	
Freezer-safe labels will be provided in specimen kits and must be used as specified in the Specimen Collection Manual. Each cryovial must be legibly labeled with: ACCL1633, COG Patient ID, Timepoint + Aliquot ID (to track individual vials), and Collection Date.
								

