Exploratory Aims 1 and 2: The sample size for the primary aim drives the overall accrual goal and thus the number of subjects available for the exploratory aims. These endpoints will be analyzed only at the end of the study, either at the end of the screening stage or confirmatory stage. Therefore, the power is estimated for the two situations separately based on sample size of 120 (60 per arm) or 454 (227 per arm) without any adjustment for power after the confirmatory stage. For Exploratory aim #1, a baseline rate of Grade II–IV aGvHD in the range of 30%–50%, the sample size after confirmatory stage is sufficient to detect a 15% reduction in aGvHD rate, while the sample size after screening stage is sufficient to detect a 20% reduction in aGvHD rate with LBP compared to placebo. Power estimation is based on 2-sample test of proportions at $\alpha=0.05$ (2-sided). For Exploratory aim #2 on serum citrulline levels, the sample size after confirmatory stage is sufficient to

detect an effect size of 0.4 standard deviation (SD), assuming we obtain samples from 80% or more of the subjects; on the other hand, the sample size after screening stage is sufficient to detect an effect size of 0.7 SD if we obtain samples from $\geq 80\%$ subjects. Power estimation is based on two-sample t-test at $\alpha=0.0125$ (2-sided), where α is based on the Bonferroni adjustment for the 4 parallel comparisons with an overall $\alpha=0.05$.

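### For the citrulline and cytokine series (exploratory Aims 2 and 5), the plan leaves the all-data mixed model optional and does not say how the repeated-measures GLM treats patients with a missing sample

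*Combined protocol and SAP*

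**What the plan says.** Section 9.3, Exploratory Aim 2, takes the mean change in citrulline "from start of conditioning to each of the four later time points" and compares the arms "via two-sample t-test and repeated-measures general linear modeling which include adjustments for potential confounders". The four comparisons, described as linear contrasts, are Bonferroni-adjusted. The section then adds: "Linear mixed models, which include data from all time points for longitudinal data analyses with adjustment for within-patient correlation, will also be considered". For the cytokines in Aim 5 it says: "We will use the same analytic approach as described for exploratory Aim 2 above".

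Section 9.4 gives the planning figures for citrulline. The confirmatory sample is sufficient to "detect an effect size of 0.4 standard deviation (SD), assuming we obtain samples from 80% or more of the subjects". At the earlier stage, "the sample size after screening stage is sufficient to detect an effect size of 0.7 SD", on the same 80% condition. These figures rest on a two-sample t-test at two-sided alpha 0.0125, with 227 or 60 patients per arm. The target power for this aim is not stated.

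Section 9.3 has no rule for missing blood samples. The rule in Section 9.2 for patients lost before their outcome is known covers GvHD outcomes only.

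Sections 7.1 and 7.4.1 schedule blood at the start of conditioning, Day 0, Day 7, Day 14, Day 28 or discharge, and Day 56, the last for citrulline alone. That makes six citrulline draws (five after baseline) and five cytokine draws (four after baseline).

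**The concern.** The longitudinal method the plan commits to is the repeated-measures GLM. In its classical univariate or multivariate form, that model needs a complete row per patient, so one missed draw removes the patient. The plan sets it beside mixed models and credits only the latter with using data from all time points. A complete-case GLM is therefore a plausible reading.

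Two things would be at stake. The first is precision: over five or six draws, modest missingness at each draw can remove a large share of patients. The second is who remains. Death, loss to follow-up and withdrawal of consent end participation (Section 8.2), and blood at Days 0 to 28 has a window of 24 hours either side. Children with complete series may well be the healthier ones, and citrulline is a marker of gut injury. That selection is plausible, but the documents do not report it.

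**Working it through.** **Inputs.** 227 and 60 per arm; 0.4 and 0.7 SD; two-sided alpha 0.05/4 = 0.0125; samples from 80% of subjects (all Section 9.4). Draws: baseline plus four (Section 9.3), or six for citrulline (Sections 7.1 and 7.4.1).

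**Step 1: reproduce the plan's figure.** Per arm, 0.8 × 227 = 181.6 and 0.8 × 60 = 48. For a two-sample t-test the noncentrality is d × √(n/2):

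- 0.4 × √(181.6/2) = 3.81, critical t 2.51, power 0.90.
- 0.7 × √(48/2) = 3.43, critical t 2.55, power 0.81.

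By the normal approximation, the detectable effects at 80% power are 0.35 and 0.68 SD, and at 85% power 0.37 and 0.72 SD. The stated 0.4 and 0.7 SD therefore reproduce as rounded values.

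**Step 2: what each method keeps, if 80% applies to each draw.** This is an assumption. Under independence, the share with k draws all present is 0.8^k. If the same 20% of patients miss everything, the share is 0.80 for any k.

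| Analysis set | Share kept | Per arm (of 227 / of 60) | Power, 0.4 SD / 0.7 SD |
|---|---|---|---|
| Same 20% miss all draws, any k | 0.80 | 182 / 48 | 0.90 / 0.81 |
| t-test on one change (k = 2), independent | 0.8² = 0.64 | 145 / 38 | 0.81 / 0.69 |
| Complete case, baseline + 4 (k = 5), independent | 0.8⁵ = 0.328 | 74 / 20 | 0.46 / 0.35 |
| Complete case, all six citrulline draws (k = 6), independent | 0.8⁶ = 0.262 | 60 / 16 | 0.37 / 0.27 |

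All powers are for a simple two-group t-test at the reduced n. They are not powers of the GLM, which also depend on covariates and on a within-patient correlation that the documents do not give.

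**Step 3: between the extremes.** With missingness linked through a shared latent factor (80% available at each draw, simulated), the complete-case loss over five draws is:

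| Latent correlation | 0 | 0.3 | 0.5 | 0.7 | 0.9 | same patients miss all |
|---|---|---|---|---|---|---|
| Loss | 67% | 56% | 49% | 41% | 31% | 20% |

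**Step 4: better availability.** At 90% per draw under independence, the loss is 1 − 0.9⁵ = 41% over five draws and 1 − 0.9⁶ = 47% over six.

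**Step 5: count of time points.** Section 9.3 has four later time points, which matches the cytokine schedule. Citrulline has five. Five contrasts would make the Bonferroni level 0.05/5 = 0.01, not 0.0125.

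**The case against.** A reader might infer that the plan restricts its longitudinal analysis to patients with every sample. The documents do not say so. A GLM with a covariance structure fitted by likelihood keeps partial series, and the remark about all time points may only contrast one joint model with four separate comparisons. This stands: complete-case fitting is one possible reading.

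A reader might also infer that two thirds of patients would be lost and that the Section 9.4 statement fails. Neither follows. The 80% is stated for subjects and as a planning floor. The 67% needs 20% missingness at every draw, independent across draws. That sits badly with the idea that sicker children miss samples, because such children would tend to miss several and the loss would then be smaller. Nor is 67% an upper bound, since six draws give 74%. The power claim rests on the t-test, and it reproduces. Section 9.4 makes no power claim for the GLM or for Aim 5, and Section 7.3.3.1 anticipates very complete laboratory data.

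Finally, a reader might infer that the arm comparison is biased. A healthier complete-case subset does not by itself bias a randomised difference. Bias would need missingness that differs by arm or acts differently on the outcome in the two arms, and nothing in the documents shows that. A mixed model also relies on a missing-at-random assumption, so it would not remove every such bias.

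These points limit the size of the problem. They do not answer the gap in specification: the all-data method is optional, the GLM's form is open, and there is no missing-sample rule.

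**Conclusion.** The concern holds as a specification gap in two exploratory aims. If the GLM is fitted in its classical form and the 80% is per draw, the complete-case loss over baseline plus four draws is 20% to 67% depending on how missingness clusters, and 74% under independence if all six citrulline draws enter. The corresponding two-group power runs from 0.90 down to about 0.46 for 0.4 SD, and from 0.81 down to about 0.35 for 0.7 SD (five draws). On the same assumptions the per-visit t-test keeps 64% to 80% of patients per contrast, with power 0.81 to 0.90 and 0.69 to 0.81. If the 80% means subjects with a full series, nothing is lost beyond what Section 9.4 already allows. Selection toward healthier children is possible but not shown. The primary endpoint and its test are untouched.

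**What to change.** In Section 9.3, name the linear mixed model on all available samples (arm, visit, arm-by-visit, baseline) as the longitudinal analysis for Aims 2 and 5, and take the Bonferroni-adjusted visit contrasts from it. State how missing samples are handled. Keep any complete-case GLM as a sensitivity analysis only.

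In Section 9.4, say whether the 80% is per draw, per baseline-and-visit pair, or for the full series. Reconcile the four later time points in Section 9.3 with the five later citrulline draws in Sections 7.1 and 7.4.1, and set the number of contrasts and the alpha to match.

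The cost is SAP wording. The model is already named in the plan, and no extra samples or patients are needed.

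### Holm's step-down method would hold the same error rate as Bonferroni for the citrulline and cytokine time-point contrasts and gain some power when several time points respond

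*Combined protocol and SAP*

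**What the plan says.** Section 9.3, Exploratory Aim 2, states that the mean change in citrulline "from start of conditioning to each of the four later time points will be compared between the 2 arms", by two-sample t-test and repeated-measures linear modelling. For these, "multiple comparison adjustments for the 4 parallel analyses (linear contrasts) will be performed with Bonferroni adjustment to maintain an overall fixed" alpha level. It adds that linear mixed models using all time points will be considered.

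For the cytokines, Exploratory Aim 5 says: "We will use the same analytic approach as described for exploratory Aim 2 above".

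Section 9.4 sets the per-contrast level at two-sided 0.0125, which "is based on the Bonferroni adjustment for the 4 parallel comparisons with an overall" alpha of 0.05. Power is considered for a "sample size of 120 (60 per arm) or 454 (227 per arm) without any adjustment for power" after the confirmatory stage, because these endpoints are analysed once, at whichever stage ends the study. The larger size is called sufficient to "detect an effect size of 0.4 standard deviation (SD), assuming we obtain samples from 80% or more of the subjects". The smaller is called sufficient for 0.7 SD under the same sampling assumption. No power value is given for this aim.

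The only purpose the plan gives for the adjustment is control of overall alpha. No stepwise method is mentioned, and no reason is given for choosing plain Bonferroni.

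**The concern.** If holding overall alpha is the only aim, a uniformly more powerful procedure meets it with the same p-values. Holm compares the smallest of four p-values with 0.05/4, the next with 0.05/3, then 0.05/2, then 0.05, and stops at the first failure. It needs no assumption about correlation.

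The difference matters when more than one contrast is non-null. Section 7.3.1 predicts a smaller fall in citrulline at Day 7 and an earlier recovery, so more than one time point may respond. Section 7.3.4 predicts lower inflammatory markers in the early post-transplant period. At stake is how many time points the trial can declare different in an exploratory analysis. No trial decision depends on it.

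**Working it through.** **Inputs from the documents.** Overall two-sided alpha 0.05, four contrasts, 227 or 60 per arm, at least 80% of samples obtained, effects of 0.4 SD and 0.7 SD (9.3 and 9.4).

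**Assumed.** The correlation between the four contrasts, because the documents give none; 0.3 to 0.6 is used below. Real effects are taken as equal in size.

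**1. The plan's own figures.**
- Per-contrast level: 0.05/4 = 0.0125, as stated. The two-sided critical value is 2.498.
- Available per arm: 0.8 × 227 = 181.6 and 0.8 × 60 = 48.
- Power ≈ Φ(d√(n/2) − 2.498).
 - 0.4 SD: 0.4 × √90.8 = 3.812; Φ(1.314) = 90.6% (90.3% by noncentral t).
 - 0.7 SD: 0.7 × √24 = 3.429; Φ(0.932) = 82.4% (80.9% by noncentral t).

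Both stated effects are detectable with at least 80% power under Bonferroni, so no stated figure needs correction.

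**2. Holm against Bonferroni.** Holm's thresholds are 0.0125, 0.0167, 0.025 and 0.05. The first equals Bonferroni's, so at least one rejection occurs under Holm exactly when it occurs under Bonferroni. Only the second and later rejections can gain.

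Four correlated z-statistics were simulated, with one to four real effects (400,000 replicates per scenario). Ranges span correlation 0.3 to 0.6.

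| Real effects | 0.4 SD, about 181 per arm: Bonferroni → Holm | 0.7 SD, 48 per arm: Bonferroni → Holm |
|---|---|---|
| One | 90.6% → 90.7% | 82.4% → 82.5% |
| Two | 90.6% → 92% | 82.4% → 84% |
| Three | 90.6% → 93–94% | 82.4% → 86–87% |
| Four | 90.6% → 95–96% | 82.4% → 89–90% |

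These are average powers per truly non-null contrast. When all four effects are real, power to reject all four goes from 72–77% to 88–90% at 0.4 SD. At 0.7 SD it goes from 54–63% to about 77–80%. Over the wider correlation range 0 to 0.8, the all-four figures are 67–82% to 87–92%, and 46–69% to 73–83%.

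**3. Error control.** With no real effects the family-wise error is identical for the two methods (3.2–4.9% over correlation 0 to 0.8). With some real effects and some nulls, Holm's maximum was 4.8%. No replicate had a Bonferroni rejection that Holm missed.

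**4. Family size.** The schedule in 7.1 and the blood-specimen table in 7.4.1 list Day 0, Day 7, Day 14, Day 28 or discharge, and Day 56 after baseline. That is five citrulline samples, against four in 9.3. If all five were tested at 0.0125, the Bonferroni bound would be 5 × 0.0125 = 0.0625; an overall 0.05 needs 0.05/5 = 0.01. Four is right for each cytokine, because the Day 56 sample is for citrulline only.

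**The case against.** Bonferroni is valid, prespecified and carried consistently into 9.4, and the aims are exploratory. A sustained effect is better addressed by the repeated-measures model, or by the mixed model that 9.3 says will be considered, than by a step-down rule on four t-tests. All of that stands, and it is why this is an improvement and not a fault.

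A reader might infer that Bonferroni gives up power for nothing. The documents do not support that. One fixed threshold serves both the tests and the power statement, and it comes with simple matching simultaneous intervals. Under Holm, a contrast with p between 0.0125 and 0.05 can be declared significant while its 98.75% interval includes zero. That is a real reporting cost, although the plan does not cite it as its reason.

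A reader might also take the four-effect row as the expected gain. Section 7.3.1 describes an effect that varies over time, not an equal shift at every visit. With one real effect the gain is negligible, and with two it is one to two points.

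**Conclusion.** A cheap improvement to an exploratory analysis. Holm gives the same family-wise error control as the planned Bonferroni adjustment under any correlation and never rejects less. The chance of at least one finding is unchanged.

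With the confirmatory sample size and 0.4 SD, per-contrast power gains about 0.1 point with one real effect, 1.4 with two, 3 with three and 4–5 with four. With the screening sample size and 0.7 SD, the corresponding gains are about 0.1, 2, 4 and 7 points. The dominance of Holm needs no assumption. The sizes rest on the plan's 80% sampling, equal real effects and an assumed correlation of 0.3 to 0.6.

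It would be wrong to infer that the plan's alpha or detectable effects are mistaken, since both reproduce. It would also be wrong to infer that the swap cures the multiplicity section. The four-versus-five count for citrulline remains open, and 9.3 states no adjustment across the several cytokines. Holm resolves neither.

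**What to change.** In 9.3, Aim 2, replace the Bonferroni adjustment with a Holm step-down adjustment at overall two-sided alpha 0.05; Aim 5 inherits it. In the same sentence, list the time points that form the citrulline family. Either name the four to be tested, or include all five scheduled after baseline, with Holm starting at 0.05/5 = 0.01.

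If four are kept, the 0.0125-based statement in 9.4 can stay, described as a lower bound. If five are chosen, restate it at 0.01. Say that Bonferroni-width simultaneous intervals will be reported and may not always agree with the Holm tests.

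The cost is one phrase and one clarifying clause, with no added patients or samples. Make the change before these endpoints are analysed, so that the choice cannot appear to follow the results.
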